The purpose of this study is to evaluate the following hypotheses in a population of CHD patients with elevated symptoms of anxiety. The present study will examine the impact of a 3-month intervention of exercise, Lexapro, or placebo on anxiety symptoms and CHD biomarkers among individuals with cardiac disease and elevated anxiety. We hypothesize the following: (1) Both exercise training and medication will reduce anxiety symptoms to a greater extent than placebo; (2) Exercise training will improve CHD biomarkers of risk including autonomic regulation, vascular endothelial function, and inflammation more than either medication or placebo; and (3) Improvements in CHD biomarkers will be mediated by reductions in symptoms of anxiety. We also will explore potential moderators of treatment (e.g., anxiety diagnoses, CHD severity) as well as the longer-term benefits of treatment by documenting medical events and health care costs over a follow-up period of up to 4 years.

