## **9. Study Interventions:**

**Randomization:** All eligible subjects will be randomly assigned to one of the 3 treatment conditions. Randomization will occur after each subject has completed the assessment protocol and will adhere to standard procedures for randomized clinical trials.[162] We will employ a conditional randomization procedure wherein equal proportion of participants with anxiety disorders will be assigned to the respective treatment groups. We also will stratify by gender (male/female), history of myocardial infarction (yes/no), and age (<60/≥60). Our anticipated sample size is 150 patients, wherein randomization will include 60 patients to Exercise Training, 60 patients to Medication, and 30 patients to Placebo. We anticipate needing to consent 300 patients in order to reach our sample size goal.

**1. Supervised aerobic exercise.** Patients will exercise three times per week, under medical supervision, at a level of 70-85% of their  $VO_{2peak}$  as determined at the time of their baseline exercise treadmill test. Patients' exercise will consist of 10 minutes of gradual warm-up exercises followed by 35 minutes of continuous walking, biking, or jogging, and 5 minutes of cool down exercises for a total a 50 minutes per session. Patients will be instructed to monitor their radial pulses and will be checked at least three times per session to ensure that they are within their prescribed exercise training ranges. Weekly supervised exercise sessions may take place at one of four sites chosen by the patient: Duke Cardiopulmonary Rehabilitation at Croasdaile, WakeMed Health and Hospitals, UNC Wellness Center at Meadowmont, and Alamance Regional Medical Center. Although depending on the geographic location of participants, other sites may be recruited for participation.

At UNC Wellness Center at Meadowmont, [name] will oversee recruitment and exercise interventions, provide active consultation and collaboration in all aspects of the study, and contribute to data analysis and manuscript writing, while [name] will assist with recruitment and oversee participation of subjects. Both investigators will have access to Duke PHI. At WakeMed, [name] and staff will work in their normal capacity to supervise patient exercise. At Alamance Regional Hospital, now owned by Cone Health, [name] will work in her normal capacity to supervise patient exercise.

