## **12. Data Management and Statistical Considerations**

**Data Analytic Approach.** The basic analytic strategy is a linear model carried out in the MPlus modeling software,[164] with treatment group contrasts as factors, and ethnicity, age, gender, and pre-treatment measure of the outcome variable as the adjustment covariables. The intent-to-treat principle (ITT) will be followed in all models, using full information maximum likelihood available in MPlus to manage missing data. For the case of the primary outcome, HADS-A, the model will include post-treatment HADS-A score as the response, with the predictors including two planned contrast variables representing 1) the two active treatments (exercise and escitalopram) vs. placebo and 2) exercise vs. escitalopram, with ethnicity, gender, age, and pre-treatment level of the HADS-A as the adjustment covariables. The contrast tests among treatment groups will be examined directly, i.e., no omnibus or “gateway” test will be required before interpreting them. In support of the HADS-A outcome, we also will compare the pattern of weekly changes in the STAI scores over time using a repeated measures model with Proc Mixed in SAS (SAS Institute, Cary, NC). The primary biomarker outcome, HRV, will be evaluated similarly. It is possible that a small number of participants may require off-protocol psychotropic medication during the course of the trial. These participants will be included in the ITT analysis and will not be replaced. We also will perform a sensitivity analysis with change in medication included as an adjustment variable in the statistical model. Finally, we will compare the treatments on the number of clinical events using a generalized linear model with the appropriate distributional form (e.g., negative binomial), using the same contrasts and covariates as in the linear model described above.

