In addition to treatment effects, we also will test the hypothesis that pre- to post-treatment change in HADS-A scores will mediate the improvements in intermediate CHD biomarkers. M-Plus allows a direct, formal test of this hypothesis via path analysis modeling. For example, a model will be specified so that both active treatment groups will be contrasted against the placebo arm, with a variable representing the change in anxiety intervening between the treatment contrast variables and post-treatment HRV (with the covariates, pre-treatment HRV, age, ethnicity, and gender). Mediation is tested by examining the product of the two component path coefficients (treatment → mediator → outcome) and its standard error, which yields the point estimate of the mediated effect along with the statistical significance of treatment on post-treatment biomarker (e.g., HRV) via change in HADS-A.[165] We also will explore possible treatment-specific mediators (e.g., change in VO2 mediating change in HRV for the Exercise group). In addition to the above tests, we will examine the impact of dropout on the estimates

of treatment effects using mixture modeling available in MPlus. Specifically, we will examine the primary outcomes using Rubin's Complier-Average Causal Effect Estimation (CACE) model,[166] which estimates the effect of treatment for all participants who adhere to the protocol irrespective of treatment group assignment. We will explore possible moderators of the treatment effect using interaction terms. Specifically, we will examine the possible moderating effects of gender, race, patient expectations, and initial severity of anxiety (e.g., DSM-5 diagnosis for an anxiety disorder); if sufficient numbers, we also plan to explore individual diagnoses by adding treatment interaction terms for these variables simultaneously with the primary model, and using a pooled test of the terms to determine whether the individual terms should be interpreted. Participants who voluntarily drop out of treatment or who are unable to complete our protocol will not be replaced but will undergo follow-up assessment.

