**Power Analysis.** Our study is powered with a focus on the primary hypothesis test: the treatment effect on anxiety as measured by HADS-A scores. We estimated power and sample size under the following assumptions: an alpha of .05, a linear model with age, gender, ethnicity, and baseline HADS-A score as covariates, a conservative estimate of the R-squared of .20 for the full model predicting post-treatment HADS-A, a 15% attrition rate, and two planned contrasts: active treatment vs. placebo and exercise vs. escitalopram. The comparison of primary interest will be active treatments vs. placebo. We estimate that a sample size of 150 (127 after attrition) will yield .80 power to detect at least a .45 SD difference between the active treatments and Placebo. In the general linear model, the exercise vs. escitalopram test will be only slightly less powered in being able to detect a .50 SD difference. In response to a previous reviewer comment, we believe that achieving this effect size is feasible. For example, in individuals with high anxiety sensitivity, Broman-Fulks[167] reported a .61 SD difference between exercisers and controls. We also re-examined data from a subset of highly anxious patients ( $STAI \geq 45$ ;  $N=32$ ) participating in our recently completed UPBEAT study[49] and found an effect size of .85 SDs on the STAI for both active treatments vs. placebo controls. We note that our power estimates are conservative in that the R-squared for the model is likely to be greater than .20 and dropout may be lower than 15%. With respect to the secondary outcome of HRV, our prior work showed that the R-squared between the baseline covariates and HRV was .73, greatly increasing the power of the tests of treatment on HRV. For the test of exercise vs. escitalopram on HRV, our primary CHD biomarker of interest, we will have a power of .80 to detect a .25 SD effect at alpha of .05. Finally, for our ancillary outcomes, including FMD, lipids, urinary catecholamines, and inflammatory markers, we have sufficient pilot data for FMD, which we use as an exemplar for power estimates: our earlier work showed that for FMD, the multiple R-squared between the baseline covariates (age, gender, ethnicity, and baseline FMD) and FMD was .50. Thus, we will have a power of .80 to detect a .34 SD effect for FMD with an alpha of .05. We estimate the power for the secondary analysis of treatment on time-to-clinical-event, assuming an event rate of 50% in the placebo group (based on unpublished data from our prior work[49]), 42 months for patient accrual, median follow-up time of 30 months and alpha = .05, is .80 to detect a reduction in event rate of 50% between both treatment groups and placebo, as well as .80 to detect a reduction in event rate of 56% between either intervention group individually and placebo. Unpublished data from our recently completed ENHANCED trial[168] revealed a 54% reduction in major adverse cardiac events among patients participating in CR compared to a matched control group of patients who did not participate in exercise-based CR.

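### The product-of-paths test of hypothesis 3 is conservative, and its example HRV equation omits baseline HADS-A; both should be changed together

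*Combined protocol and SAP*

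**What the plan says.** Hypothesis 3 in Section 2 reads: "Improvements in CHD biomarkers will be mediated by reductions in symptoms of anxiety". Section 12 (Data Analytic Approach) makes it testable by expecting that "pre- to post-treatment change in HADS-A scores will mediate the improvements in intermediate CHD biomarkers". Its worked example is a path model with "the change in anxiety intervening between the treatment contrast variables and post-treatment HRV (with the covariates, pre-treatment HRV, age, ethnicity, and gender"). On the test itself: "Mediation is tested by examining the product of the two component path coefficients" (treatment to mediator to outcome) "and its standard error, which yields the point estimate of the mediated effect along with the statistical significance".

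The general model at the start of the same section adjusts for demographic variables and the "pre-treatment measure of the outcome variable as the adjustment covariables".

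The text leaves four things open:
- the standard error formula and reference distribution (no bootstrap, distribution-of-product or other asymmetric interval is mentioned);
- whether change is raw or residualised;
- whether baseline HADS-A enters the HRV equation;
- whether the active arms are pooled or each compared with placebo.

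No power is stated for mediation. The Power Analysis concerns HADS-A: the planned sample "will yield .80 power to detect at least a .45 SD difference between the active treatments and Placebo". On allocation, "randomization will include 60 patients to Exercise Training, 60 patients to Medication, and 30 patients to Placebo".

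**The concern.** A product of two estimates is not normally distributed in a sample of this size. Referring it to a normal distribution through its standard error gives too few rejections when either path is modest. The trial has only about 25 evaluable placebo patients, so power for hypothesis 3 is scarce and this choice gives some of it away.

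The covariate gap is separate. The general rule supplies the baseline of whatever variable is the response. It can put baseline HADS-A into the mediator equation, but in the HRV equation it supplies only baseline HRV. Change in HADS-A is correlated with its own baseline. If baseline anxiety has its own effect on later HRV, the mediator path picks it up.

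At stake is the reading of one of three stated hypotheses: a real mediated effect missed or, in the less likely setting, a significant effect in the wrong direction.

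**Working it through.** **Inputs from the documents (Section 9; Section 12, Power Analysis).** Evaluable patients: 150 × .85 = 127.5, taken as 127. By arm: 60 × .85 = 51, 51, and 30 × .85 = 25.5, taken as 25. Treatment effect on anxiety (path a): .45 SD, with .61 and .85 SD from the two supporting studies cited there. R-squared .20 for HADS-A, all given to baseline HADS-A, so the pre-post correlation is √.20 = .45. R-squared .73 for HRV, so residual variance is .27. Alpha .05, taken as two-sided.

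**Assumed, because the documents do not give them.** Mediator path b = .05 to .4 SD of HRV per SD of HADS-A (absolute size), a partial correlation √(.8b²/(.8b² + .27)) of .09 to .57. Baseline-to-post SD ratio of HADS-A k = 1 to .6. Pooled active arms against placebo (102 vs 25), except in step 3.

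The plan has no mediation figure to reproduce.

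**Step 1. Why the test is conservative.** With the usual standard error,

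z = ab / √(a²SE_b² + b²SE_a²) = z_a z_b / √(z_a² + z_b²),

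which is always below the smaller of z_a and z_b. If both paths sit exactly at 1.96, z = 1.96/√2 = 1.39 (p = .17).

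For a = .45 and b = .2:
- SE_a = √.8 × √(1/102 + 1/25) = .894 × .223 = .200, so z_a = 2.25.
- SE_b = √(.27/(127 × .8)) = .0516, so z_b = 3.88.
- z = 2.25 × 3.88 / √(2.25² + 3.88²) = 1.95.

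Even with both paths estimated at their assumed values, the test just misses 1.96.

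**Step 2. Simulated power, baseline HADS-A in both equations** (HRV follows anxiety at both visits, k = .8, 4,000 trials per cell; estimate/SE, then product interval):

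| b | a = .45 | a = .61 | a = .85 |
|---|---|---|---|
| .05 | .025, .084 | .053, .118 | .095, .151 |
| .10 | .106, .245 | .198, .354 | .342, .457 |
| .15 | .267, .456 | .461, .660 | .664, .783 |
| .20 | .399, .555 | .662, .802 | .892, .943 |
| .30 | .535, .594 | .806, .849 | .978, .984 |
| .40 | .568, .600 | .828, .847 | .983, .986 |

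At .45 SD the gap is 6, 14, 19, 16, 6 and 3 points. With only the listed covariates it is nearly the same (5, 14, 18, 15, 6 and 3). At b = 0, estimate/SE rejects 0.5%, 1.1% and 2.3% for a = .45, .61 and .85; other runs gave up to about 2.5% at .85.

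**Step 3. Contrast coding.** With each active arm against placebo (51 vs 25), power at a = .45, b = .2 falls to about .35 to .38 for estimate/SE and .49 to .53 for the product interval.

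**Step 4. Baseline HADS-A left out of the HRV equation.** Let g be the direct effect of baseline HADS-A on post-treatment HRV given baseline HRV. With raw change as mediator, the bias in b is g × cov(baseline, change)/var(change). With equal SDs and pre-post correlation r this is g × (r − 1)/(2(1 − r)) = −g/2. So g = −.10 gives +.05 and g = −.20 gives +.10; simulation returned .05 and .10.

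Share of the true mediated effect recovered, k = 1/.8/.6:
- HRV follows the change (g = 0): 99/99/101%.
- HRV follows anxiety at both visits: 93/96/98%.
- Post-treatment HRV follows the post-treatment level only (g = b): 50/70/87%. The 50% agrees with the −g/2 formula.

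Baseline HADS-A in the mediator equation alone leaves these shares essentially unchanged. In both equations they are 98 to 100% throughout.

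Two-sided rejection with true b = 0 and a = .85 (lower figure k = .8, upper figure equal SDs; the last two rows are equal SDs only):

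| HRV equation | Test | g = −.10 | g = −.20 |
|---|---|---|---|
| Listed covariates | estimate/SE | 6 to 9% | 20 to 35% |
| Listed covariates | product interval | 11 to 18% | 30 to 52% |
| Baseline HADS-A in both equations | estimate/SE | 2.6% | 2.8% |
| Baseline HADS-A in both equations | product interval | 4.9% | 5.0% |

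At a = .45 with equal SDs, estimate/SE with the listed covariates rejects 1.9% and 9.0%. Here the spurious b is positive while treatment lowers anxiety, so the product says that falling anxiety lowers HRV. That is the reverse of hypothesis 3.

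**The case against.** A conservative test is valid, so part of this is a preference between methods. That stands. The gain is also narrow: 3 points at b = .4 and .45 SD, and 2 points or less at .85 SD once b reaches .25. The documents give no value for b.

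Estimate/SE is inferred from silence. The plan cites a methods source for the test but names neither the formula nor the reference distribution. The reading is natural, and the power loss is conditional on it.

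The covariate list is introduced as an example, so the final model may include baseline HADS-A. That also stands; nothing in the text puts it there.

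Three stronger readings are tempting, and the documents do not support them:
- That a non-significant result will be reported as absence of mediation. No rule in the plan says so.
- That omitting baseline HADS-A seriously distorts the mediation estimate. This needs a direct effect of baseline anxiety on later HRV given baseline HRV, which the documents give no reason to expect.
- That the omission could manufacture support for hypothesis 3. With higher baseline anxiety going with lower later HRV, the direction the background section suggests, the spurious effect has the wrong sign.

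The opposite reading, that the only risk is a missed effect, is not safe either, as step 4 shows.

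**Conclusion.** The point holds and is minor. If the model is correctly specified and the test is estimate/SE, it rejects about 0.5% to 2.5% at b = 0 for effects of .45 to .85 SD. It gives up roughly 6 to 19 points of power at .45 SD for b of .05 to .3. These sizes are illustrative: b is assumed, the main figures use the pooled contrast, and separate contrasts give lower power.

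The covariate omission is harmless or nearly so if HRV follows anxiety change or anxiety at both visits. It matters only under the direct effect described, where two-sided error at .85 SD reaches about 6 to 9% and 20 to 35% for assumed effects of −.10 and −.20 SD.

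No primary conclusion or stated power rests on this test. Mediation power also stays limited by the treatment-to-anxiety path: z_a = 2.25 gives power of only about .6 with 102 vs 25, so even the better interval reaches only about .55 to .58 at .45 SD and b = .2. That this path falls short of the plan's stated .80 is a separate matter.

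**What to change.** Make these changes together in Section 12:
- Test the indirect effect with a percentile-bootstrap 95% confidence interval, or a distribution-of-product interval.
- Include baseline HADS-A in both the mediator and HRV equations, and likewise baseline VO2 where VO2 change is the mediator.
- State whether change is raw or residualised, and whether the active arms are pooled or each compared with placebo.

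Do not adopt the product interval without the covariate: in the direct-effect setting that raises the error, as step 4 shows.

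The cost is a few lines of text and code and one degree of freedom per equation. The measures are already scheduled at baseline and 3 months. Where raw change is already nearly unbiased, at .45 SD and b = .2, adding baseline HADS-A to the HRV equation as well as the mediator equation costs 0 to 3 points of power with the product interval and up to 7 with estimate/SE. The loss can be larger when the treatment path is strong and b small: at .85 SD and b = .10, with equal SDs and HRV following change, product-interval power falls from .565 (listed covariates) to .458.

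Type I error at b = 0 for .45/.61/.85 SD, with the covariate in both equations, was 2.3/4.1/5.6% for the product interval and 2.0/5.0/4.7% for the percentile bootstrap. The product interval can therefore sit slightly above 5% when the treatment path is strong.

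### The design gives about 62% power, not 80%, for the .45 SD active-versus-placebo difference; the HRV (.25 SD) and FMD (.34 SD) figures also fail on the plan's own inputs

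*Combined protocol and SAP*

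**What the plan says.** All the power claims are in section 12, Power Analysis. The main contrast is named: "The comparison of primary interest will be active treatments vs. placebo". The inputs are given as "We estimated power and sample size under the following assumptions: an alpha of .05", "a conservative estimate of the R-squared of .20 for the full model predicting post-treatment HADS-A" and 15% attrition. The result is that "a sample size of 150 (127 after attrition) will yield .80 power to detect at least a .45 SD difference". The second contrast follows: "the exercise vs. escitalopram test will be only slightly less powered in being able to detect a .50 SD difference".

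For HRV, with R-squared .73 and the contrast given as exercise versus escitalopram, the plan says "we will have a power of .80 to detect a .25 SD effect at alpha of .05". For FMD, with R-squared .50 and no contrast named, it says "we will have a power of .80 to detect a .34 SD effect for FMD with an alpha of .05".

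The power paragraph mentions neither the allocation ratio nor whether alpha is one- or two-sided. The allocation is in section 9, Randomization: "60 patients to Exercise Training, 60 patients to Medication, and 30 patients to Placebo". Section 10 confirms that placebo is 30 patients, or 20%.

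**The concern.** Pooling two arms of 60 against one of 30 is a 4:1 comparison, and its precision is governed mainly by the small placebo arm. Exercise versus escitalopram is a balanced 60:60 comparison. With the same residual variance, the balanced contrast is the more precise of the two here, yet the plan presents it as the weaker one.

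The sample size rests on the .45 SD sentence. If it is wrong, the chance of missing a true .45 SD effect is nearly twice the 20% that the plan implies, and a null primary result could be read as stronger evidence against such an effect than it is. The plan's own background shows why this range matters. One pooled exercise effect cited in section 3 is .48 SD, which lies above the claimed .45 but below what the design can detect with 80% power. That estimate compares exercise with untreated controls, so it is indicative only.

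**Working it through.** **Inputs.** 150 randomised 60/60/30 (section 9). 15% attrition leaves 150 × .85 = 127.5, which the plan gives as 127. Split 2:2:1, that is 50.8 / 50.8 / 25.4. R-squared is .20 (HADS-A), .73 (HRV) and .50 (FMD), and alpha is .05, all from section 12. Two-sided testing is an assumption, tested below.

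**Formulas.** In total-SD units, SE = √(1 − R²) × √(1/n₁ + 1/n₂). The effect detectable with 80% power is (1.960 + 0.842) × SE. Power at effect d is Φ(d/SE − 1.960).

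**A figure that reproduces: exercise versus escitalopram on HADS-A.**
- SE = √.80 × √(1/50.8 + 1/50.8) = .894 × .198 = .177.
- Detectable effect = 2.802 × .177 = .497 SD, matching the stated .50. Power at .50 is .80.
- With one-sided alpha the detectable effect would be .44 SD and power at .50 would be .88. The plan's convention therefore appears to be two-sided, after attrition, in total-SD units.

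**Primary contrast: active versus placebo on HADS-A.**
- SE = √.80 × √(1/101.6 + 1/25.4) = .894 × .222 = .198.
- Detectable effect = 2.802 × .198 = .556 SD, against the stated .45.
- Power at .45: Φ(.45/.198 − 1.960) = Φ(.31) = .62. A non-central t calculation gives .61.

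**What would give .45?** All rows use R-squared .20.

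| Variant | Power at .45 SD | Detectable effect (SD) |
|---|---|---|
| 2:2:1, 127 completers, two-sided | .62 | .56 |
| 2:2:1, no attrition (120 vs 30), two-sided | .69 | .51 |
| 2:2:1, 127 completers, one-sided | .73 | .49 |
| 1:1:1, 127 completers, two-sided | .76 | .47 |
| 2:2:1, no attrition, one-sided | .79 | .454 |
| Two equal halves of 127, two-sided | .81 | .445 |

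Only the last two rows come close. The one-sided, no-attrition row contradicts the stated 127 and does not fit the .50 SD figure. The equal-halves row fits the 127, the R-squared and the two-sided convention, but not the allocation.

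**R-squared needed.** For .45 SD to hold at 2:2:1 with 127 completers: 1 − R² = (.45/2.802)² / (1/101.6 + 1/25.4) = .0258/.0492 = .524, so R-squared would have to be about .48. Power is .68 at R-squared .30 and .74 at .40.

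**HRV, exercise versus escitalopram, R-squared .73.**
- SE = √.27 × .198 = .103. Detectable effect = .29 SD; power at .25 SD is .68.
- Check that does not depend on sidedness: this is the same contrast as the .50 SD figure, so only the residual SD changes. .50 × √(.27/.80) = .29, not .25.

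**FMD, R-squared .50.**
- Exercise versus escitalopram: SE = √.50 × .198 = .140; detectable effect .39 SD; power at .34 SD is .68.
- Active versus placebo: SE = √.50 × .222 = .157; detectable effect .44 SD; power at .34 SD is .58.

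**Size needed for the claim as written.** At 2:2:1, 80% power for .45 SD needs 195 completers (78/78/39), or 195/.85 ≈ 230 randomised.

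**The case against.** Four points can be made for the plan.

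1. **Sidedness is not stated, and the biomarker hypothesis is directional.** At one-sided .05 with about 51 per arm, the detectable effects are .256 SD for HRV and .35 SD for FMD, with power .78 at the stated values. That is close. But one-sided testing does not rescue the primary figure (.73) and spoils the .50 SD figure that otherwise fits. Nor can it reconcile the .50 and .25 figures, which concern the same contrast: their ratio is .50, while the two R-squared values require √(.27/.80) = .58.

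2. **The cause is not proven.** This stands. No formula is given, and a one-sided calculation without attrition comes about as near to .45 as equal halves do. Neglect of the 4:1 split is the better-fitting explanation, but an inference. It also does not explain HRV, which is a balanced contrast, or FMD: even equal halves of 127 give only .77 for either. Those are separate discrepancies.

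3. **The assumptions are described as conservative.** Higher R-squared or lower dropout would narrow the gap. Zero attrition gives only .69, though, and R-squared would have to be more than double the assumed value.

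4. **Feasibility does not rest on .45 SD alone.** The plan cites effects of .61 and .85 SD, for which this design has power of about .87 and .99. This stands, and it supports keeping the design. It does not make the .45 SD statement true.

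The biomarker figures also carry less weight: the plan treats HRV as secondary and FMD as ancillary.

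**Conclusion.** The primary power statement is wrong as written. On the plan's own N, attrition, allocation and R-squared, with two-sided alpha .05, active versus placebo has about 62% power at .45 SD and 80% power at .56 SD. The chance of missing a true .45 SD effect is about 38%, not 20%. No choice of sidedness brings the figure to 80% with 127 completers at 2:2:1.

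The .50 SD figure for exercise versus escitalopram is correct, so the ordering of the two contrasts is reversed in the text. The HRV and FMD figures are also not met: .29 SD rather than .25, and .39 or .44 SD rather than .34. The absolute biomarker values assume two-sided testing. The inconsistency between the HRV figure and the .50 SD figure does not.

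**What to change.** Keep N = 150 and the 2:2:1 allocation, and rewrite the power paragraph:

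- State that alpha is two-sided and that the calculation uses about 102 active and 25 placebo completers. If one-sided testing was intended, say so and recompute every figure on that basis.
- HADS-A, active versus placebo: 80% power for .56 SD, and 62% at .45 SD.
- HADS-A, exercise versus escitalopram: keep .50 SD, and delete the statement that this is the less powered test.
- HRV, exercise versus escitalopram: .29 SD.
- FMD: name the contrast, and give .39 SD (exercise versus escitalopram) or .44 SD (active versus placebo).

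The cost is one paragraph and less favourable detectable effects. No patients, visits or analyses change. Keeping the .45 SD claim instead would take about 230 randomised patients at the present ratio.
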